9.0 Study Visits

Baseline Visit

Signed Informed Consent is to be obtained prior to the conduct of any study procedures. Baseline information consists of collection of participant demographics, hearing and pertinent medical history, hearing history (i.e. etiology and onset of hearing loss, date of birth, gender, duration of hearing loss, amplification use). With respect to amplification use, the licensed/certified hearing care professional will determine if a potential study participant has had an adequate and/or appropriate trial using conventional amplification available for single-sided deafness and asymmetrical hearing loss.

The following test measures are administered at the Baseline Visit:

Audiometric Testing:

- Unaided air-conduction thresholds using insert earphones at 250, 500, 1000, 2000, 4000 and 8000 Hz; unilateral, each ear. Clinical masking as appropriate.
- Unaided bone-conduction hearing thresholds at 500, 1000, 2000 and 4000 Hz; unilateral, each ear

Speech Perception Testing:

- Separate Ear CNC Word Test Two lists of 50 words tested in the participant's everyday listening condition for that ear, thus:
 - If the test ear is unaided (participant does not utilize conventional amplification such as a hearing aid, CROS, BICROS or osseointegrated system), measurement of CNC words using insert earphones presented at 60 dBA will be conducted.
 - If the test ear is aided with conventional amplification (i.e. hearing aid, CROS, BICROS or osseointegrated system), measurement of CNC words is conducted in soundfield at 60 dBA (Target 0° Azimuth) with the plug and muff method in use for the non-test ear (better hearing ear) to eliminate from potential cross-over and/or contribution to the outcome.
- AzBio Sentence Test in Noise Two lists presented in the following soundfield conditions at 60 dBA with a +5 dB SNR using speech-spectrum noise in the participant's bilateral, everyday listening condition. Note: Participants may or may not be aided in one or both ears thus, testing may be aided or unaided or a combination during AzBio Sentence test administration). The following test conditions will be conducted:

- Speech Front, Noise Front (Target and Noise 0° azimuth)
- Speech Front (0° azimuth), Noise directed to the ear to be implanted (90° or 270° azimuth)
- Speech Front (0° azimuth), Noise directed to the contralateral/non-implanted ear (90° or 270° azimuth)

Lateralization Testing:

Using AzBio Sentence Test in Quiet - One list presented at 40 dBA in soundfield in the
participant's bilateral, everyday listening condition. The participant is asked to identify if
the sentence was detected from the left or right speaker. The sentence delivery from
right or left speaker is randomized.

Note: Participants may or may not be aided in one or both ears thus, testing may be aided or unaided or a combination during test administration). The test setup is as follows:

• Participant will be centered and faced forward between a right and left speaker (each positioned in corners of the audiometric suite at 45° respectively)

Self-Assessment Questionnaire(s):

- Speech, Spatial and Sound Qualities (SSQ) Questionnaire standard version (Version 5.6)
- Tinnitus Handicap Inventory (THI) Administered only if participant has reported tinnitus
- Sponsor developed patient report questionnaire/scale

Implant Surgery:

Conducted at participant's managing hearing care clinical center. Note: Implant surgery to be completed within 26 weeks of the Baseline Visit. If the surgery date exceeds this time frame, Baseline measures including audiometric and speech perception testing will need to be reevaluated.

Initial Device Activation/Fitting:

Device activation should occur within 3 to 6 weeks postimplant surgery.

Device Programming – Sound Processor Fitting: Specific Instruction:

 Study participants are to be provided with a standard everyday program with the following FDA approved signal processing strategy(ies):

HiRes™ Optima with ClearVoice

Additional programs and parameter settings are deferred to the guidance and recommendations of the participant's managing hearing care specialist.

Audiometric Testing:

- Unaided air-conduction thresholds using insert earphones at 250, 500, 1000, 2000, 4000 and 8000 Hz; unilateral, each ear. Clinical masking as appropriate.
- Unaided bone-conduction hearing thresholds at 500, 1000, 2000 and 4000 Hz;
 unilateral, each ear

Adverse Event Assessment:

An adverse event assessment is completed by the investigator at each test interval. An assessment will be completed additionally if an adverse event has occurred outside of the scheduled study test intervals (i.e. unscheduled visit).

3 and 6 Month Postimplant Test Intervals:

The three and six month post-device activation visits to occur within 12 and 24 weeks respectively (+/- 14 days) of the participant's device activation date.

Important Note: The participant is to be tested at each scheduled study test interval using the standard everyday program (HiRes™ Optima program with ClearVoice).

Please confirm that this program is selected prior to testing.

Speech Perception Testing:

- CNC Word Test in Quiet Two lists of 50 words presented at 60 dBA in the *implanted ear only* (plug and muff method to be used in the contralateral/non-implanted ear
 during testing)
- AzBio Sentence Test in Noise Two lists presented in the following soundfield conditions at 60 dBA with a +5 dB SNR using speech-spectrum noise in the participant's everyday, bilateral listening condition. The following test conditions will be conducted:
 - Speech Front, Noise Front (Target and Noise 0° azimuth)
 - Speech Front (0° azimuth), Noise directed to the implanted ear (90° or 270° azimuth)
 - Speech Front (0° azimuth), Noise directed to the non-implanted ear (90° or 270° azimuth)

Lateralization Testing:

AzBio Sentence Test in Quiet - One list presented at 40 dBA in soundfield in the
participant's everyday bilateral listening condition. The participant is asked to identify if
the sentence was detected from the left or right speaker. The sentence delivery from
right or left speaker is randomized.

Note: Participants may or may not be aided in one or both ears thus, testing may be aided or unaided or a combination during test administration). The test setup is as follows:

• Participant will be centered and faced forward between a right and left speaker (each positioned in corners of the audiometric suite at 45° respectively)

Self-Assessment Questionnaire(s):

- The Speech, Spatial and Sound Qualities Questionnaire SSQ-B (Version 5.6) is to be administered at the 3 and 6 month test intervals
- Tinnitus Handicap Inventory (THI) Administered only if participant has reported tinnitus
- Glasgow Benefit Inventory
- Sponsor developed patient report questionnaires/scales

Adverse Event Assessment:

An adverse event assessment is completed by the investigator at each test interval. An assessment will be completed additionally if an adverse event has occurred outside of the scheduled study test intervals (i.e. unscheduled visit).

Device Re-Programming (if necessary)

 Adjustment/optimization of participant's device program as recommended by managing clinician.

12 Month Postimplant Test Interval:

The twelve month post-device activation visit to occur within 48 weeks (+/-14 days) of the participant's device activation date.

Important Note: The participant is to be tested at each scheduled study test interval using the standard everyday program ().

Please confirm that this program is selected prior to testing.

Audiometric Testing:

- Unaided air-conduction thresholds using insert earphones at 250, 500, 1000, 2000, 4000 and 8000 Hz; unilateral each ear. Clinical masking as appropriate.
- Unaided bone-conduction hearing thresholds at 500, 1000, 2000, and 4000 Hz;
 each ear.

Speech Perception Testing:

• CNC Word Test in Quiet - Two lists of 50 words presented at 60 dBA in the *implanted* ear only

- AzBio Sentence Test in Noise Two lists presented in the following soundfield conditions at 60 dBA with a +5 dB SNR using speech-spectrum noise in the participant's everyday, bilateral listening condition. The following test conditions are to be conducted:
 - Speech Front, Noise Front (Target and Noise 0° azimuth)
 - Speech Front (0° azimuth), Noise directed to the implanted ear (90° or 270° azimuth)
 - Speech Front (0° azimuth), Noise directed to the non-implanted ear (90° or 270° azimuth)

Lateralization Testing:

AzBio Sentence Test in Quiet - One list presented at 40 dBA in soundfield in the
participant's bilateral, everyday listening condition. The participant is asked to identify if
the sentence was detected from the left or right speaker. The sentence delivery from
right or left speaker is randomized.

Note: Participants may or may not be aided in one or both ears thus, testing may be aided or unaided or a combination during test administration. The test setup is as follows:

• Participant will be centered and faced forward between a right and left speaker (each positioned in corners of the audiometric suite at 45° respectively)

Self-Assessment Questionnaire(s):

- Important Note: The Speech, Spatial and Sound Qualities Questionnaire standard SSQ version (5.6) is administered at this test interval.
- The Tinnitus Handicap Inventory (THI) Administered only if participant has reported tinnitus
- Glasgow Benefit Inventory
- Sponsor developed patient report questionnaire/scale

Adverse Event Assessment:

An adverse event assessment is completed by the investigator at each test interval. An assessment will be completed additionally if an adverse event has occurred outside of the scheduled study test intervals (i.e. unscheduled visit).

Device Re-Programming (if necessary)

• Adjustment/optimization of participant's device program as recommended by managing clinician.

9.1 Summary of Data Collection at Study Test Intervals:

Test Measure/ Activity	Condition	Preoperative	Postoperative Intervals			
		Baseline	Initial Device Activation	3 Month	6 Month	12 Month
Informed Consent		X				
Demographics and Hearing History		Х				
Objective					2	
Measures	e e e e e e e e e e e e e e e e e e e				4	2
Unaided Audiometric Testing (Air/Bone Conduction)	Unilateral, each ear	х	х			х
CNC Words – Quiet 60 dBA	Unilateral, each ear	х		200		
Skirre-Endo-Stri	Treated Ear			X	X	Х
AzBio Sentences – Noise (60 dBA + 5 dB SNR)	Bilateral Listening Condition/ Everyday Listening Condition	X		X	х	X
Lateralization Task using AzBio Sentences in Quiet – 40 dBA	Bilateral Listening Condition/ Everyday Listening Condition	х		х	х	х
Subjective		9			9	0.0
Measures	e.				4	
SSQ		Х		Х	Х	Х
GBI		3		Х	X	Х
THI ¹	8	X		Х	х	X
Sponsor developed patient report questionnaire/scale		Х		х	Х	х

¹Participants that do not report tinnitus pre or postoperatively are not administered the THI questionnaire.

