8.3 Test Metrics or Procedures

The monosyllabic CNC word test will be used as the primary test metric for preimplant candidacy determination and follow-up postimplant performance assessments in the treated ear. The AzBio Sentence test in noise will be used as the primary test metric to assess the binaural hearing condition (implanted + non-implanted ear) performance pre-to-postoperatively.

Given the asymmetrical clinical population for which this feasibility study is being conducted, standard audiometric clinical masking procedures during audiometric and speech perception metrics will be applied as needed to reduce any potential contribution of the better hearing ear during these assessments.

In order to isolate the ear to be implanted and/or treated ear during certain test conditions (i.e. aided testing), a foam earplug and an over-the-head earmuff will be used in the contralateral (non-implanted ear). This method will be referred to in the remainder of this document as 'plug and muff.'

8.3.1 Audiometric Measures:

Standard audiometric practice and procedures are applied for the testing of inter-octave frequencies if necessary.

[figure not shown]
- Unaided air conduction thresholds using insert earphones at octave frequencies will be obtained for each ear at 250, 500, 1000, 2000, 4000 and 8000 Hz. Clinical masking used as appropriate.
- Unaided bone conduction hearing thresholds for each ear at 500, 1000, 2000 and 4000 Hz

8.3.2 Speech Perception Measures:

General speech perception testing procedures

All speech perception testing will be conducted using recorded stimuli presented from a single loudspeaker in at a minimum a single-walled sound booth capable of accommodating a calibrated, 90 degree speaker orientation. Audiometers will conform to ANSI standards for pure-tone and speech audiometry and/or Manufacturer Specifications.

Speech perception measures conducted in soundfield are to be administered via a loudspeaker at 0° azimuth at a distance of one meter from the subject. Speech signals will be presented at 60 dB A. Speech levels will be calibrated to 60 dB SPL using a microphone placed at the approximate position of the subject's head (one meter from loudspeaker).

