IMPORTANT NOTE REGARDING POSTOPERATIVE TESTING: Audiometric and speech perception testing at post device activation intervals is to be conducted prior to any device re-programming and/or adjustment of MAP parameters. It is recommended that a listening check of the participant's device and confirmation of sufficient battery life be verified prior to testing at each study interval.

Consonant-Nucleus-Consonant (CNC) Word Recognition Test

The CNC monosyllabic word test (Peterson and Lehiste, 1962) is a validated test of openset word recognition ability. The test will be administered in quiet at 60 dBA (target 0° azimuth) and scored as total number of words correct which will be expressed for results/reporting as percentage correct. The CNC word test is the primary speech perception metric used for study inclusion determination and postoperative outcome comparison at defined intervals for this feasibility study.

AzBio Sentence Test

The AzBio Sentence Test (Spahr and Dorman, 2005) is a validated test of open-set sentence recognition ability. The test is scored as total number of words correct which is expressed for results/reporting as percentage correct. The sentence test tokens include

both male and female speakers. The AzBio Sentence test will be administered at 60 dBA + 5 dB SNR in noise using Speech-spectrum Noise (SSN) in three conditions:

- Speech Front, Noise Front (Target and noise 0° azimuth)
- Speech Front (0° azimuth), Noise directed to the *ear to be implanted/implanted* ear (90° or 270° azimuth)
- Speech Front (0° azimuth), Noise directed to the non-implanted ear (90° or 270° azimuth)

Lateralization Testing

The AzBio Sentence test will additionally be used as the metric to assess lateralization. The test will be administered in soundfield in quiet at 40 dBA. The participant will be positioned face-forward and centered between the right and left speakers (located at 45°) and at a one meter distance (typical calibrated test position) in the audiometric sound suite. A single list of interleaved sentences varying between right and left speaker presentations will be administered. The participant will be asked to identify if the sentence is heard from the right or left speaker. Scoring is based on number correct that the participant identifies from which speaker the sentence was detected.

8.3.3 Patient Questionnaire(s):

Speech, Spatial and Sound Qualities Questionnaire (SSQ)

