11.0 Efficacy Measures

Collection of efficacy data to support product approval is not part of this feasibility study. As such, no formal statistical hypothesis is being posed and/or applied. As part of this feasibility study, the following data will be collected and evaluated:

- Monosyllabic word recognition performance in quiet using the CNC word test pre-to
 post device activation at 12 months will be compared, tabulated and summarized.
 Specifically, the CNC word scores postoperatively will be compared to the pre-implant
 word score for the implanted ear. Individual and group comparisons will be completed.
 The intent is to understand the benefit of the implant treatment option and restoration
 of auditory input results in improved speech understanding.
- 2. Audiometric hearing thresholds at the 12 month postoperative test interval will be compared to preimplant thresholds. Individual and group comparison is confirmatory to assess that hearing acuity in the non-implanted ear (better hearing ear) is not affected significantly by cochlear implant treatment in the opposite ear (poorer hearing ear).
- 3. Sentence recognition scores in noise using the AzBio Sentence Test pre-to-post device activation will be compared, tabulated and summarized. Specifically, the everyday, bilateral listening condition AzBio sentence scores at the 12 month postimplant test interval will be compared to the preimplant bilateral sentence score. Individual and group comparisons will be conducted. The intent of this comparison is to evaluate the contribution and/or benefit of the implant treatment option (provision of binaural sensory input) in an asymmetrical hearing loss population.
- 4. To understand if the restoration of binaural sensory input in a single-sided deafness/asymmetrical hearing loss population results in improved ability in lateralization of sound. Using the AzBio Sentence metric, the month postimplant outcome will be compared to preoperative ability. Individual and group comparisons will be conducted.

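### For ears unaided before surgery, CNC delivery and better-ear isolation differ between baseline and follow-up, and plug and muff is not stated at the 12-month endpoint visit

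*Combined protocol and SAP*

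**What the plan says.** The general rules are in Section 8.3. Section 8.3.2 states: "All speech perception testing will be conducted using recorded stimuli presented from a single loudspeaker". Its CNC paragraph adds "The test will be administered in quiet at 60 dBA (target 0° azimuth"), which describes soundfield testing. For isolation, Section 8.3 says that "during certain test conditions (i.e. aided testing), a foam earplug and an over-the-head earmuff will be used in the contralateral (non-implanted ear"). It also allows clinical masking when needed in speech tests, to limit the better ear's contribution, but gives no trigger or level.

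Section 9.0 makes the baseline CNC method depend on whether the test ear is aided. For an unaided ear, "measurement of CNC words using insert earphones presented at 60 dBA will be conducted". An aided ear is tested in soundfield "with the plug and muff method in use for the non-test ear (better hearing ear"). At 3 and 6 months the instruction for the implanted ear is explicit: "plug and muff method to be used in the contralateral/non-implanted ear". At 12 months the bullet reads only "Two lists of 50 words presented at 60 dBA in the *implanted* ear only".

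Section 11.0 item 1 sets the comparison at 12 months: "Specifically, the CNC word scores postoperatively will be compared to the pre-implant" score in the implanted ear. Section 10.0 plans no hypothesis test. It asks at least for counts of subjects who improved, stayed the same or got worse.

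**The concern.** CNC in the treated ear is the main measure of implant benefit, and each subject is his or her own control (Section 7.1). That design removes differences between people, but not a change of test method that happens at the same time as surgery.

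For a subject unaided at baseline in the poorer ear, the words are first fed directly into that ear. After surgery they come from a loudspeaker that both ears face, with the better ear shut out by a foam plug and a muff. Under Section 7.4 the better ear must score above 30% on CNC and has no lower limit on hearing loss, so it can be near normal. The ear to be implanted must score 30% or less. Any speech that reaches the better ear through the isolation after surgery would be scored as if the implant had heard it.

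At stake are the mean CNC change and the improved / unchanged / worse counts. No formal test or sample-size calculation depends on them.

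**Working it through.** **Step 1. The CNC instructions side by side (Section 9.0).**

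| Visit | Delivery | Better-ear isolation stated at that visit |
|---|---|---|
| Baseline, test ear unaided | Insert earphones, 60 dBA | None in the bullet; general masking rule only |
| Baseline, test ear aided | Soundfield, 60 dBA, 0° | Plug and muff |
| 3 and 6 months | 60 dBA, implanted ear | Plug and muff |
| 12 months | 60 dBA, implanted ear | None in the bullet; plug and muff by inference from Section 8.3 |

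The first row conflicts with Section 8.3.2. The calibration described there uses a microphone at the head position, one metre from the loudspeaker, and does not cover insert delivery. Subjects in the second row have the 3- and 6-month isolation method at baseline too, so they are not affected.

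**Step 2. Is leakage plausible?** The plan gives no size or attenuation figure, so there is nothing to reproduce. Assume plug-and-muff attenuation A of 25 to 60 dB. The level reaching the better ear is 60 − A, that is, 35 down to 0 dBA. Some recognition is plausible for a near-normal better ear at the upper end, and negligible for a poor ear or high attenuation.

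**Step 3. Additive upper bound on the mean.** Let f be the share of subjects unaided at baseline, and L_post and L_pre the CNC points added by the better ear. The bias in mean gain is f × (L_post − L_pre). All inputs are assumed.

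| Net leakage (points) | f = 0.25 | f = 0.5 | f = 1.0 |
|---|---|---|---|
| 0 | 0 | 0 | 0 |
| 5 | 1.25 | 2.5 | 5 |
| 10 | 2.5 | 5 | 10 |
| 20 | 5 | 10 | 20 |

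**Step 4. Why this is an upper bound.** A word that the implant already recognises cannot be credited twice. With implant-ear score p, leakage L and independent recognition (an assumption), the observed score is p + L − pL. With L = 20%:
- Implant ear 50%: 0.50 + 0.20 − 0.10 = 60%, so leakage adds 10 points, not 20.
- Implant ear 30%: 0.30 + 0.20 − 0.06 = 44%, so leakage adds 14 points.

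**Step 5. Effect on individual counts.** Take 100 words (two lists of 50), a true score of 5% at both times, and leakage added after surgery only. Exact binomial probabilities are:

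| Leakage (points) | P(any observed gain) | P(gain of 10 points or more) |
|---|---|---|
| 0 | 0.435 | 0.001 |
| 5 | 0.890 | 0.112 |
| 10 | 0.990 | 0.544 |

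Section 10.0 sets no threshold for improvement, so small leakage could move these counts. At so low a score the overlap in Step 4 hardly matters: 5 + 5 − 0.25 = 9.75%, against 10% used here.

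**Step 6. What a matched baseline would do.** Let p0 and p1 be the true scores before and after surgery.
- Gain against an uncontaminated insert score: (p1 − p0) + L(1 − p1), too high.
- Gain against a matched score with the same L: (p1 − p0)(1 − L), too low.

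With p0 = 5%, p1 = 50%, L = 20%, the true gain is 45. The insert comparison gives 60 − 5 = 55 (+10). The matched baseline is 5 + 20 − 1 = 24%, so the matched comparison gives 60 − 24 = 36 (−9). With p1 = 30% the true gain is 25, and the two comparisons give 39 (+14) and 20 (−5). The two gains bracket the truth if p1 is at least p0, leakage is equal at both times, the insert score is free of better-ear contribution, and the two delivery methods otherwise score the ear alike.

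**The case against.** The insert baseline has a design reason. Section 9.0 tests each ear in its everyday condition, and an ear using a sound processor cannot repeat an insert-earphone test after surgery. Section 8.3 also provides masking for speech tests without limiting it to a visit or transducer. The study is a small feasibility study, descriptive only and not meant to support approval. All of this stands, and it limits the weight of the point. It does not make the two scores comparable.

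Several stronger readings are tempting, but the documents do not support them.
- *Every postoperative CNC uses plug and muff.* It is explicit only at 3 and 6 months. The gap at 12 months matters more, because an unplugged better ear would contribute more.
- *Better-ear speech can enter only the postoperative score.* The documents do not say that insert delivery excludes cross-over, and masking is available at any visit with its use unspecified.
- *The subjects with the best contralateral hearing are exactly those affected.* The rule turns on whether the test ear is aided. A subject with a normal better ear who uses a CROS or osseointegrated device counts as aided and has plug and muff at baseline.
- *The overstatement can be given a figure.* Assuming 3 to 8 affected subjects of 15 and 5 to 20 points of leakage gives 3 × 5/15 = 1.0 to 8 × 20/15 = 10.7 points. Both inputs are invented and the range leaves out zero. With the overlap in Step 4 at a 50% implant score, the top falls to 8 × 10/15 = 5.3.
- *Swapping the insert score for a soundfield one would cancel the problem.* Step 6 shows that it can over-correct. It would also change the entry test: with 20 points of leakage, a true 15% ear scores 15 + 20 − 3 = 32% and misses the 30% limit.

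**Conclusion.** The point holds in a limited form. For subjects whose ear to be implanted is unaided before surgery, the 12-month CNC comparison mixes two delivery and isolation methods. The change coincides with implantation, and a design without a control group cannot separate the two. The general loudspeaker rule and the insert baseline contradict each other, the endpoint visit omits plug and muff, and the masking rule has no trigger or level.

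The likely direction of any error is towards a larger gain. Its size cannot be derived from the documents and may be about zero if attenuation is high, the better ear is poor, or few subjects are unaided. The figures in Steps 3 to 6 show sensitivity to assumed inputs and are not estimates for this trial. The remedy is cheap and worth making, but the defect does not invalidate the study.

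**What to change.** 1. Reconcile Sections 8.3, 8.3.2 and 9.0. If the insert-earphone test stays, name it as an exception to the loudspeaker rule and say how its 60 dBA level is calibrated.
2. In the Section 9.0 Baseline Visit, keep the insert score for eligibility. For an unaided ear to be implanted, also obtain CNC in soundfield at 60 dBA, 0° azimuth, with plug and muff (and any masking) on the better ear as at follow-up.
3. In Section 11.0 item 1, report the gain against the matched score next to the gain against the insert score, split by baseline test mode. Present the two as a bracket, under the conditions in Step 6. A matched score well above the insert score in the same ear points to better-ear leakage, and shows it before surgery.
4. In the 12-month CNC bullet, state plug and muff on the better ear. Give one masking rule, with trigger and level, for all visits, and record when it is used.

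The cost is two extra 50-word lists at baseline for subjects with an unaided ear to be implanted. The booth and method are already used for aided ears. The 30% entry criterion is untouched. The stated gain may be somewhat smaller.
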